## **8.6.2** Statistical Methods for Safety Analyses

Safety and tolerability will be assessed by clinical review of all relevant parameters including AEs, laboratory tests, and vital signs. The treatment comparisons or treatment differences in this section pertain to the MK-0653H (EZ 10 mg + Ros 2.5 mg, or EZ 10 mg + Ros 5 mg) versus corresponding monotherapy components [i.e., EZ 10 mg and Ros (2.5 or 5 mg)].

The analysis of safety results will follow a tiered approach. The tiers differ with respect to the analyses that will be performed. Safety parameters or adverse experiences of special interest that are identified a priori constitute "Tier 1" safety endpoints that will be subject to inferential testing for statistical significance with p-values for treatment comparisons as well as point estimates and corresponding 95% CIs for between-group differences. Other safety parameters will be considered Tier 2 or Tier 3. Tier 2 parameters will be assessed via point estimates and corresponding 95% CIs provided for between-group differences; only point estimates by treatment group are provided for Tier 3 safety parameters.

AEs (specific terms as well as SOC terms) that are not pre-specified as Tier 1 endpoints will be classified as belonging to "Tier 2" or "Tier 3", based on the number of subjects who experiences the events. Membership in Tier 2 requires that at least 4 subjects in any treatment group exhibit the event; all other AEs will belong to Tier 3.

The threshold of at least 4 events was chosen because the 95% CI for the between-group difference in percent incidence will always include zero when treatment groups of equal size each have less than 4 events and thus would add little to the interpretation of potentially meaningful differences. Because many 95% CIs may be provided without adjustment for multiplicity, the CIs should be regarded as a helpful descriptive measure to be used in review, not a formal method for assessing the statistical significance of the between-group differences in AEs.

Continuous measures such as changes from baseline in laboratory and vital signs parameters that are not pre-specified as Tier 1 endpoints will be considered Tier 3 safety parameters. Summary statistics for baseline, on-treatment, and change from baseline values will be provided by treatment group in table format.

Refer to Table 5 for a list of safety endpoints by tier.

p-Values (Tier 1 only) for treatment comparisons and 95% CIs for between-treatment differences in the percentage of subjects with respective Tier 1 and Tier 2 events will be

MK-0653H-832-01 Final Protocol Confidential 04RWM

**Protocol/Amendment No.:** 832-01

calculated using the Miettinen and Nurminen method. The analysis will not be stratified by risk category.

**Protocol/Amendment No.:** 832-01

Table 5 Analysis Strategy for Safety Parameters

Safety		p-	95% CI for	Descriptive
tier	Safety endpoint †	Value	treatment difference	statistics
Tier 1	
 
gastrointestinal related AEs
 
gallbladder-related AEs
 
allergic reaction or rash AEs
 
hepatitis-related AEs
 
consecutive elevations in ALT ≥3x ULN
 
consecutive elevations in AST ≥3x ULN
 
consecutive elevations in ALT or AST ≥3x ULN
 
ALT or AST ≥5x ULN
 
AST elevations ≥5x ULN
 
ALT or AST elevations ≥5x ULN
 
ALT elevations ≥10 x ULN
 
AST elevations ≥10x ULN
 
ALT or AST elevations ≥10x ULN
 
potential Hy's Law condition (ALT or AST elevations >3x ULN, with ALP <2x ULN and TBL ≥2x ULN)
 
CK elevations ≥10x ULN
 
CK elevations ≥10x ULN with muscle symptoms
 
CK elevations ≥10x ULN with muscle symptoms that are considered drug-related
 
	X	X	X
Tier 2	
 
AE
 
drug-related AE
 
SAE
 
drug-related SAE
 
discontinuation due to AE
 
discontinuation due to drug-related AE
 
discontinuation due to SAE
 
discontinuation due to drug-related SAE
 
specific AEs, SOCs (incidence ≥4 subjects in at least one treatment group)
 
Specific AEs, or SOCs‡ (incidence <4
 
		X	X
	
 
subjects in all treatment groups)
 
Change from baseline results (laboratory, and vital signs)
 
			X
' AE re	ferences refer to both clinical and laboratory AEs.			

AE references refer to both clinical and laboratory AEs.

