# 4.2.2.3 Safety Endpoints

The safety will be evaluated with clinical and laboratory safety assessments conducted throughout the study.

Clinical measurements to assess the safety and tolerability of MK-0653H include monitoring of AEs and clinical evaluation (including vital signs and physical examination).

Laboratory safety assessments include chemistry, hematology and urinalysis, performed at specific study visits. All determinations will be performed by the central laboratory.

Gastrointestinal related AEs, gallbladder-related AEs, allergic reaction or rash AEs, hepatitis-related AEs, consecutive elevations in ALT and/or AST  $\geq 3x$ ULN, ALT and/or AST elevation  $\geq 5x$ ULN, ALT and/or AST elevation  $\geq 10x$ ULN, Potential Hy's Law Condition (defined as serum ALT or serum AST elevations  $\geq 3x$ ULN, with serum alkaline phosphatase <2xULN and total bilirubin (TBL)  $\geq 2x$ ULN), elevations in CK  $\geq 10x$ ULN, elevations in CK  $\geq 10x$ ULN with muscle symptoms that are considered drug-related are determined as safety events of special interest (Tier1 events) and will be evaluated.

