# 5.8 Subject Withdrawal/Discontinuation Criteria

Subjects may withdraw consent at any time for any reason or be dropped from the trial at the discretion of the investigator should any untoward effect occur. In addition, a subject may be withdrawn by the investigator or the Sponsor if enrollment into the trial is inappropriate, the trial plan is violated, or for administrative and/or other safety reasons. Specific details regarding discontinuation or withdrawal procedures are provided in Section 7.1.4 – Other Procedures.

Table 2 provides reasons why a subject must be discontinued from treatment but may continue to be monitored in the trial, as well as reasons why a subject must be discontinued from treatment and the trial.

Table 2 Discontinuation Scenarios

Reason for Discontinuation Scenario	Action				
The subject or legal representative (such as a parent	Discontinuation from Treatment and Trial				
or legal guardian) withdraws consent.					
The subject's treatment assignment has been	Discontinuation from Treatment and Trial				
unblinded by the investigator, Merck subsidiary or					
through the emergency unblinding call center					
Consecutive (2 or more measurements) elevations in	Discontinuation from Treatment and Trial				
ALT and/or AST $\geq 3 \times ULN$					
Consecutive elevations in CK $\geq$ 10 x ULN with or	Discontinuation from Treatment and Trial				
without muscle symptoms.					
Consecutive elevations in CK $\geq$ 5 to <10 x ULN	Discontinuation from Treatment and Trial				
with muscle symptoms.					
Subject requiring any treatment with cyclosporine	Discontinuation from Treatment and Trial				
or fibrates.					
Pregnancy (Positive serum pregnancy test): A	Discontinuation from Treatment and Trial				
positive urine pregnancy test requires immediate					
interruption of study drug while awaiting results of					
serum pregnancy (β-hCG) test.					
Any subject who is unblinded to treatment regimen	Discontinuation from Treatment and Trial				
during study. (The subject's treatment assignment					
has been unblinded by subject him/herself.)					
Adverse experiences: Subject may be withdrawn	Discontinuation from Treatment and Trial				
from the study in the event that the investigator					

04REM Confidential

Protocol/Amendment No.: 832-01

Reason for Discontinuation Scenario	Action
assesses that administration of the study drug should	
be discontinued due to the occurrence of adverse	
experiences which would interfere with study	
continuation.	

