3. Myopathy or Rhabdomyolysis are to be reported as ECI because of their association with lipid-lowering treatments. If a subject is reported as having myopathy, rhabdomyolysis, or if the CPK criterion necessitating study medication discontinuation is met, this constitutes an ECI. ECIs will be recorded in the database, monitored by the SPONSOR and reported in the clinical study report.

**Protocol/Amendment No.:** 832-01

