#### 2. Actions

- Patients with persistent (2 or more) CK elevations between 5 and <10 times the ULN and muscle symptoms will also be discontinued.
- Patients with persistent (2 or more) CK elevations between 5 and <10 times the ULN without symptoms may remain on drug (at the discretion of the SPONSOR medical monitor) with more intensive monitoring (as agreed to by the monitor and investigator). These patients should remain on drug until repeat labs are obtained.
- Patients with persistent (i.e., 2 consecutive measurements), unexplained 10 fold elevation in CK with or without symptoms will be discontinued from the study.

NOTE: All discontinued patients should be monitored and have repeat lab draws completed until critical elevations have resolved.

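### No muscle-specific Tier 1 row covers the protocol's own stopping level of CK 5 to <10x ULN with muscle symptoms

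*Combined protocol and SAP*

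**What the plan says.** **Tier 1 rows.** Section 8.6.2 makes Tier 1 endpoints "subject to inferential testing for statistical significance with p-values for treatment comparisons as well as point estimates and corresponding 95% CIs". For muscle, Table 5 lists any CK ≥10x ULN, then "CK elevations ≥10x ULN with muscle symptoms", then "CK elevations ≥10x ULN with muscle symptoms that are considered drug-related". Section 4.2.2.3 uses the same floor. It names CK ≥10x ULN and the symptomatic, drug-related subset, but not the middle row.

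**Stopping rules.** Table 2 (Section 5.8) has two CK scenarios that end treatment and trial participation: consecutive CK ≥10x ULN with or without symptoms, and consecutive CK 5 to <10x ULN with muscle symptoms. Appendix 12.6 repeats the second: "Patients with persistent (2 or more) CK elevations between 5 and <10 times the ULN and muscle symptoms will also be discontinued".

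**Events of clinical interest.** Section 7.2.3.2, item 3, says "Myopathy or Rhabdomyolysis are to be reported as ECI because of their association with lipid-lowering treatments", and adds that "if the CPK criterion necessitating study medication discontinuation is met, this constitutes an ECI". ECIs are to be recorded, monitored by the sponsor and reported in the study report. No between-group comparison of them is specified.

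**Other tiers.** Tier 2 has fixed rows for discontinuation because of any AE and because of a drug-related AE, each with a 95% CI and no p-value. Specific AE terms and system organ class (SOC) terms enter Tier 2 only if at least 4 subjects in some arm have them. Otherwise they are Tier 3, with point estimates by arm only.

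**The concern.** Primary objective 3 is the safety and tolerability of the two combinations. The protocol treats symptomatic CK elevation from 5x ULN upward as serious enough to stop treatment and to report within 24 hours as an ECI. The pre-specified muscle comparisons start only at 10x ULN. A combination arm could have several stops under the lower CK rule and still show 0 v 0 in all three Tier 1 muscle rows, which a reader of the study report could take as absence of a muscle signal. A muscle row at the stopping level that is first chosen after unblinding would be post hoc under Section 8.0.

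**Working it through.** **1. Stopping rules against Tier 1 rows**

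| Stopping rule (Table 2, Appendix 12.6) | Tier 1 row that counts it (Table 5) |
|---|---|
| Consecutive ALT and/or AST ≥3x ULN | Yes: consecutive ALT or AST ≥3x ULN |
| Consecutive CK ≥10x ULN, with or without symptoms | Yes: CK ≥10x ULN, which does not even require consecutive values |
| Consecutive CK 5 to <10x ULN with muscle symptoms | None, unless some value reaches 10x ULN |

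Myopathy or rhabdomyolysis reported without CK ≥10x ULN also has no Tier 1 muscle row.

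**2. Where such a subject does appear**

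- In the ECI reporting (7.2.3.2, item 3), with no comparison specified.
- In the Tier 2 rows for discontinuation due to any AE or a drug-related AE, if the stop is recorded as an AE. The Table 5 footnote includes laboratory AEs. These rows carry a 95% CI without a minimum count, but pool all causes.
- In a specific AE term or SOC, with a CI only from 4 subjects in one arm.

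**3. Arm sizes.** Section 8.9 randomizes 306 at 1:2:2:2:2. Then 306/9 = 34 for ezetimibe and 2 × 34 = 68 for each other arm.

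**4. The plan's own figure.** Section 8.6.2 justifies the threshold of 4 by stating that the CI always includes zero when equal arms each have fewer than 4 events. The Miettinen-Nurminen test of zero difference is

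z = (x₁/n₁ − x₂/n₂) / √[ p̄(1 − p̄)(1/n₁ + 1/n₂) · N/(N − 1) ], with p̄ = (x₁ + x₂)/N and N = n₁ + n₂.

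- 3 v 0 at 68 v 68: p̄ = 3/136 = 0.0221, difference 3/68 = 0.0441, standard error 0.0253, z = 1.745, p = 0.081.
- 4 v 0 at 68 v 68: p̄ = 4/136 = 0.0294, difference 4/68 = 0.0588, standard error 0.0291, z = 2.023, p = 0.043.

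The threshold is reproduced. At 62 v 62 the p-values are 0.081 and 0.043 as well.

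**5. Illustration with assumed counts.** The documents give no rate for symptomatic CK 5 to <10x ULN. Suppose k subjects in a combination arm are stopped under that rule without reaching 10x ULN, and none in the matching rosuvastatin arm (68 v 68).

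| k | Contribution to each Tier 1 CK row as written | p if one row covered the stop |
|---|---|---|
| 1 | 0 v 0 | 0.317 |
| 2 | 0 v 0 | 0.156 |
| 3 | 0 v 0 | 0.081 |
| 4 | 0 v 0 | 0.043 |
| 5 | 0 v 0 | 0.023 |

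Against ezetimibe (68 v 34), 7 v 0 gives p = 0.054 and 8 v 0 gives 0.038.

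**6. Power of such a row, under assumed true rates (68 v 68, two-sided 0.05).** About 3% for 2% v 0.5%, and about 24% for 5% v 1%.

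**The case against.** - **These subjects are compared already.** In part this stands. A reader might infer that they go unanalysed or fall to Tier 3 with no comparison. The documents do not support that: the two Tier 2 discontinuation rows carry a CI with no minimum count, and different muscle terms can pool within an SOC and reach 4 there. But the discontinuation rows pool all causes and an SOC row pools a whole organ class, so neither isolates the muscle stop.
- **A rising CK will be caught.** This also stands in part. It is tempting to say that the rule removes subjects before CK can reach 10x ULN. However, Appendix 12.6 requires a retest within 3 days and repeat draws after discontinuation, and the ≥10x row needs only one value. The gap concerns subjects who never reach 10x ULN.
- **The event is rare and the test weak.** True, as steps 5 and 6 show. The existing ≥10x rows describe still rarer events, however, and the sponsor ranks them Tier 1.
- **A rate can be borrowed.** Section 4.1.2 gives 2.26% for drug-related CK increase. That is any such increase over 52 weeks in a mixed post-marketing population, with no CK level, symptom or repeat requirement. It also is not listed among the most common events in the rosuvastatin co-administration group. It does not size this event.
- **Tier 1 need not mirror the stopping rules.** Nothing in the plan says that it must, so the CK floor is partly a choice. The liver rows show the sponsor choosing to compare arms at the stopping level.

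**Conclusion.** The point holds in a limited form. One of the two CK stopping scenarios has no matching Tier 1 row, so a subject stopped for consecutive CK 5 to <10x ULN with muscle symptoms, and never reaching 10x ULN, enters no muscle-specific Tier 1 comparison. This rests on the definitions and needs no assumed rate. The loss is a pre-specified, muscle-specific estimate and CI. It is not a loss of reporting or of all comparison, provided the stop is recorded as an AE for the Tier 2 rows. How many subjects are affected cannot be derived from the documents, and few are likely at 68 (34 for ezetimibe) per arm. This is a cheap improvement to a table that serves a primary objective. It does not affect the efficacy conclusions.

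**What to change.** Add one row to Table 5 and to Section 4.2.2.3: any ECI under 7.2.3.2, item 3 (myopathy, rhabdomyolysis, or a CK discontinuation criterion met). State that both CK scenarios of Table 2 count. Analyse it by Miettinen-Nurminen, either as Tier 1 or as a named Tier 2 row with a CI only and no 4-subject threshold. A separate row for consecutive CK ≥5x ULN with symptoms is unnecessary, because this row largely contains it. Keep the ≥10x rows, and bring the CK lists in 4.2.2.3 and Table 5 into line. No clinical rule changes.

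The data already exist as ECIs and central-laboratory CK. Section 8.0 lets a non-confirmatory analysis change be documented in the supplemental SAP before unblinding. The cost is one more unadjusted row. Table 5 has 17 Tier 1 rows read over four treatment comparisons (17 × 4 = 68 p-values), which would become 18 × 4 = 72. The Tier 2 option adds CIs but no p-values.

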## 8.6.3 Summaries of Baseline Characteristics, Demographics, and Other Analyses

The comparability of the treatment groups for each relevant characteristic will be assessed by the use of tables and/or graphs. No statistical hypothesis tests will be performed on these characteristics. The number and percentage of subjects screened, randomized, the primary reasons for screening failure, and the primary reason for discontinuation will be Demographic variables, baseline characteristics, primary and secondary diagnoses, and prior and concomitant therapies will be summarized by treatment either by descriptive statistics or categorical tables.

## **Interim Analyses**

No interim analyses are planned for the study.

<sup>‡ Includes only those endpoints not pre-specified as Tier 1 or Tier 2 endpoints.

**Protocol/Amendment No.:** 832-01

## 8.8 Multiplicity

The study has two families of primary hypotheses, each comparing one arm of MK-0653H (i.e., EZ 10 mg + Ros 2.5 mg, or EZ 10 mg + Ros 5 mg) to the corresponding monotherapy components [i.e., EZ 10 mg and Ros (2.5 or 5 mg)]. Successful demonstration of a family of primary hypotheses requires superiority of MK-0653H to both EZ and Ros, and hence, no adjustment for multiplicity within a family of primary hypotheses is required. Multiplicity across the two families of primary hypotheses will be adjusted by the Hochberg procedure, which is implemented as follows.

[figure not shown]
Let  $p_{1E}$  and  $p_{1R}$  be the p-values associated with the treatment comparisons of EZ 10 mg + Ros 2.5 mg to EZ 10 mg and to Ros 2.5 mg, respectively, and  $p_{1max}$  be the larger of  $p_{1E}$  and  $p_{1R}$ . Define  $p_{2E}$ ,  $p_{2R}$  and  $p_{2max}$  similarly for the treatment comparisons of EZ 10 mg + Ros 5 mg to EZ 10 mg and to Ros 5 mg.

Let  $p_{Fmax}$  and  $p_{Fmin}$  be the larger and smaller of  $p_{1max}$  and  $p_{2max}$ , respectively. Then the conclusions of the study will be as follows, depending on the values of  $p_{Fmax}$  and/or  $p_{Fmin}$ :

- if  $p_{Fmax} \le 0.05$ , then both of the two families of primary hypotheses are considered successfully demonstrated
- if  $p_{Fmax} > 0.05$  and  $p_{Fmin} \le 0.025$ , then only the family of primary hypotheses associated with  $p_{Fmin}$  is considered successfully demonstrated but the other family is not
- otherwise, neither of the two families of primary hypotheses is considered successfully demonstrated.

A schematic display of multiplicity adjustment is shown in Figure 2 below.

#### p-Values

#### **Decision strategy**

[figure not shown]

Figure 2 Schematic Display of Multiplicity Adjustment

MK-0653H-832-01 Final Protocol

**Protocol/Amendment No.:** 832-01

## 8.9 Sample Size and Power Calculations

A total of 306 subjects will be randomized in a ratio of 1:2:2:2:2 to the following 5 arms: EZ 10 mg, Ros 2.5 mg, Ros 5 mg, MK-0653H (EZ 10 mg + Ros 2.5 mg), MK-0653H (EZ 10 mg + Ros 5 mg). Assuming that valid LDL-C measurements can be obtained at Week 12 from 31 subjects in the EZ 10 mg arm and from 62 subjects in each of the other 4 arms, the study will have a power of approximately 97% to successfully demonstrate both of the two families of primary hypotheses at  $\alpha$ =0.05, two-sided. For each of the two families of primary hypotheses, the study will have a power of approximately 97% that the family of primary hypotheses can be demonstrated at  $\alpha$ =0.025, two-sided. The study will have a probability of approximately 98% to show a numerically greater LDL-C percent reduction at Week 12 with MK-0653H (EZ 10 mg + Ros 5 mg) compared with MK-0653H (EZ 10 mg + Ros 2.5 mg). These calculations were performed using simulations. Power calculations for pairwise comparisons are shown in Table 6 below.

Table 6 Power Calculations for Pairwise Comparisons

Endpoint	N 1	$N_2$	Minimum detectable difference with 90% power $[\alpha=0.05 (0.025), \text{ two-sided}]$	Half-width of 95 (97.5) % CI	SD
LDL-C % change	62	62	9.4 (10.2) %	5.7 (6.5) %	16%
	62	31	11.5 (12.6) %	7.0 (8.0) %	16%

The calculations shown in Table 6, and the calculations above performed using simulations, are based on the assumptions on the true percent change from baseline in LDL-C at Week 12 for each treatment arm as shown in Table 7, and a true SD of 16%. These are conservative estimates from previously conducted factorial studies with EZ 10 mg and statins, as well as placebo-controlled monotherapy studies with EZ 10 mg or Rosuvastatin.

Table 7 Assumptions on True LDL-C Percent Change from Baseline by Treatment

Ezetimibe	Rosuvastatin			
Ezetimide	0 mg	2.5 mg	5 mg	
0 mg		-34%	-40%	
10 mg	-15%	-46%	-52%	

#### 8.10 Subgroup Analyses and Effect of Baseline Factors

To determine whether the treatment effect is consistent across various subgroups, the estimate of the between-group treatment effect (with a nominal 95% CI) for the primary endpoint will be estimated and plotted within each category of each subgroup.

- age category (<65 years, ≥65 years)
- gender (male, female)
- prior lipid-lowering agent therapy [none, treatment with a statin (with or without other lipid-lowering agent therapies), treatment without a statin]
- diabetes mellitus (yes, no)
- hypertension (yes, no)
- baseline LDL-C ( $\leq$  or > median)
- risk category (category I, category II, category III)

**Protocol/Amendment No.:** 832-01

The consistency of the treatment effect will be assessed using the same model as the primary efficacy analysis model.

## **8.11 Compliance (Medication Adherence)**

A day within the study will be considered an "On-Therapy" day if the subject takes one tablet / capsule each from Bottle A and Blister cards B and C. For a subject who is followed for the entire study period, the "Number of Days Should be on Therapy" is the total number of days from the day of randomization to the last scheduled day for treatment administration for that subject. For a patient who discontinued from the study permanently, the "Number of Days Should be on Therapy" is the total number of days from the day of randomization to the date of the last dose of study medication.

For each subject, percent compliance will be calculated using the following formula:

(Number of Days on Therapy / Number of Days Should be on Therapy) x 100.

Summary statistics will be provided on percent compliance by treatment group for the FAS population.

#### **8.12** Extent of Exposures

The dose level and treatment duration will be summarized for the ASaT population.

# 9.0 LABELING, PACKAGING, STORAGE AND RETURN OF CLINICAL SUPPLIES

## 9.1 Investigational Product

The investigator shall take responsibility for and shall take all steps to maintain appropriate records and ensure appropriate supply, storage, handling, distribution and usage of investigational product in accordance with the protocol and any applicable laws and regulations.

Clinical Supplies will be provided by the Sponsor as summarized in Table 8.

